1.4.2. Blinding

This is a single-blind study. Subjects, Investigators and other site personnel administering study drug, performing the clinical assessments, and handling data on the study subjects, will be blinded to individual subject treatments assignments (ie, ABI-H2158+ETV or PBO+ETV) throughout the duration of the study. The CRO and Sponsor study team responsible for study execution will also remain blinded to mitigate any potential operational bias. A DRC, comprising a limited number of internal Sponsor members who are independent of the study team, will be unblinded to individual subjects' treatment assignments for the prespecified safety data reviews (see Section 2.1).

2. TYPE OF PLANNED ANALYSIS

2.1. DRC Interim Analyses

An internal DRC will perform regular unblinded reviews of safety data to ensure timely analysis of any emergent safety/tolerability issues, and completion of the prespecified safety data reviews. As this is an exploratory Phase 2a study, the DRC will also assess the unblinded HBV virology parameter (HBeAg, HBsAg, HBcrAg, HBV DNA and HBV pgRNA) results at prespecified timepoints before the final analysis to make strategic decisions relating to drug development. The aggregated virology data may be released for external communication.

The initial DRC review will be conducted after approximately 25% of planned enrolled subjects in Cohort 1 have completed at least 4 weeks of treatment. Additional meetings will be scheduled approximately every month. In addition to regular review of safety and virology data, the DRC will also review the interim PK analysis when all randomized subjects in each cohort or approximately 2-5 subjects from South Korean sites, have completed Week 4 assessments or discontinued before completing Week 4.

The DRC will comprise Sponsor's representatives from Clinical Research and Biometrics. Other functional area members may be included as necessary. The DRC's role and responsibilities and the scope of the analysis will be provided in a charter, which will define the DRC membership, meeting logistics, and meeting frequency. The DRC members will not be directly involved in the study conduct and will not have interactions with the study sites. The unblinded study results they may review and the meeting minutes, along with any decisions or recommendations made, will be archived in a secure location. All other Sponsor personnel will remain blinded until completion of the study.

The study remains blinded following the study termination. The DRC meetings are held to review and monitor the safety data after study drug discontinuation before the study unblinding.

2.2. Final Analysis

As of 01 September 2021, the study is early terminated. The final analysis to support a 'Synoptic Clinical Study Report' will be performed after all subjects have discontinued or completed the 12-week follow-up visits, outstanding data queries have been resolved or adjudicated as unresolvable, and the data have been cleaned and finalized.

3. GENERAL CONSIDERATIONS FOR DATA ANALYSES

Analysis results will be presented using descriptive statistics. For categorical variables, the number and percentage of subjects in each category will be presented. For continuous variables, the number of subjects (n), mean, standard deviation (SD) or standard error (SE), median, first quartile (Q1), third quartile (Q3), minimum, and maximum will be presented.

Given that the study is early terminated, no formal statistical testing will be performed.

By-subject listings will be presented for all subjects in the All Randomized Analysis Set and sorted by subject identification (ID) number, visit date, and time (if applicable) in chronological order within the subject. The treatment group to which subjects were randomized will be used in the listings.

3.1. Analysis Sets

Analysis sets define the subjects to be included in an analysis. Analysis sets and their definitions are provided in this section. The analysis set will be identified and included as a subtitle of each table, figure, and listing. For each analysis set, the number and percentage of subjects eligible for inclusion will be summarized by treatment group. A listing of reasons for exclusion from analysis sets will be provided by subject.

3.1.1. All Randomized Analysis Set

All Randomized Analysis Set includes all subjects who were randomized in the study, classified according to the treatment group into which they were randomized regardless of the actual treatment received.

3.1.2. Full Analysis Set

The Full Analysis Set (FAS) includes all randomized subjects, classified according to the treatment group into which they were randomized regardless of the actual treatment received who took at least 1 dose of study drug. This is the primary analysis set for efficacy analyses.

3.1.3. Safety Analysis Set

The Safety Analysis Set includes all subjects, classified according to the actual treatment received regardless of random assignment, who took at least 1 dose of study drug. This is the primary analysis set for safety analyses.

3.2. Subject Grouping

For analyses based on the All Randomized Analysis Set and FAS, subjects will be grouped according to the treatment to which they were randomized. For analyses based on the Safety Analysis Set, subjects will be grouped according to the actual treatment received. The actual

treatment received will differ from the randomized treatment only when their actual treatment differs from randomized treatment for the entire treatment duration.

3.3. Strata and Covariates

Subjects will be randomly assigned to treatment groups via IRT in a 3:1 ratio to receive either 300 mg ABI-H2158+ETV (n=30) versus matching PBO+ETV (n=10) using a stratified randomization schedule. Stratification will be based on the HBV DNA level measured at the Screening visit as follows:

- For Cohort 1, HBV DNA level measured at the Screening visit, $\geq 8.0 \log_{10}$ IU/mL versus $< 8.0 \log_{10}$ IU/mL.
- For Cohort 2, HBV DNA level measured at the Screening visit, $\geq 6.0 \log_{10}$ IU/mL versus $< 6.0 \log_{10}$ IU/mL.

If there are discrepancies in stratification factor values between the IRT and the clinical database, the values recorded in the clinical database will be used for analyses.

3.4. Data Handling Conventions and Transformations

Subject age collected at Screening visit will be used for analyses and presented in listings. The age is derived in the electronic data capture (EDC) system based on the year of birth and informed consent date.

In general, laboratory data that are continuous in nature but are less than the lower limit of quantitation (LLOQ) or above the upper limit of quantitation (LOQ) will be imputed to the value of the lower or upper limit minus or plus 1 significant digit, respectively (eg, if the result of a continuous laboratory test is < 20 , a value of 19 will be assigned).

- A value that is 1 unit less than the LLOQ will be used to calculate descriptive statistics if the datum is reported in the form of " $<x$ " (where x is considered the LOQ). For example, if the values are reported as < 50 and < 5.0 , values of 49 and 4.9, respectively, will be used to calculate summary statistics. An exception to this rule is any value reported as < 1 or < 0.1 , etc. For values reported as < 1 or < 0.1 , a value of 0.9 or 0.09, respectively, will be used to calculate summary statistics.
- A value that is 1 unit above the upper LOQ will be used to calculate descriptive statistics if the datum is reported in the form of " $>x$ " (where x is considered the LOQ). Values with decimal points will follow the same logic as above.
- The LOQ will be used to calculate descriptive statistics if the datum is reported in the form of " $\leq x$ " or " $\geq x$ " (where x is considered the LOQ).

For selected analyses, virology efficacy data will be transformed to the logarithmic (base 10) scale (\log_{10} IU/mL).

Total bilirubin values entered as <0.2 mg/dL will be analyzed as 0.1 mg/dL; direct bilirubin values entered as <0.1 mg/dL will be analyzed as 0.05 mg/dL (according to the methods of Nehls and Akland, 1973).

3.5. Missing Data and Outliers

3.5.1. Missing Data

In general, missing data will not be imputed unless methods for handling missing data are specified. Exceptions are presented in this document.

For missing last dose date of study drug, imputation rules are described in Section 4.2.1. The handling of missing efficacy data is described in Section 6. The handling of missing or incomplete dates for AE onset is described in Section 7.1.5.2.

3.5.2. Outliers

Outliers will be identified during the data management review process. No sensitivity analyses will be conducted. All data will be included in the data analysis.

3.6. Analysis Visit Windows

3.6.1. Definition of Study Day

In this study, study drug is defined as ABI-H2158 (or matching PBO) and ETV.

The first dose date of ABI-H2158/PBO and of ETV will be calculated. Study Day 1 is defined as the first dose date of study drug, which is the minimum of the first dose dates of ABI-H2158/PBO and ETV in a treatment group. If the first dose date is missing, the date of randomization will be used.

The last dose date of ABI-H2158/PBO and of ETV will be calculated. The last dose date for each drug will be the end date on the respective “Subject Disposition: End of the Treatment” eCRF. The last dose date of study drug will be defined as the maximum of the last dose dates of ABI-H2158/PBO and ETV in a treatment group.

Study day will be calculated from Study Day 1 and derived as follows:

- For days prior to the first dose: Assessment Date – Study Day 1
- For postdose study days: Assessment Date – Study Day 1 + 1

For the follow-up period, the follow-up Study Day 1 is defined as the day after the last dose date of ABI-H2158/PBO and the follow-up study day will be calculated from the last dose date and derived as Assessment Date – Last Dose Date of ABI-H2158/PBO.

3.6.2. Analysis Visit Windows

Subject visits might not occur on protocol-specified days. Therefore, for the purpose of analysis, observations will be assigned to analysis windows. In general, the baseline value will be the last nonmissing value on or prior to the first dose date of study drug. The “on-treatment” period is defined up to the last dose date of ABI-H2158/PBO. The “off-treatment” period is defined after the last dose of ABI-H2158/PBO through the follow up period.

The assessment schedule is different in the Korea country specific protocol amendment. The analysis window will follow what is specified in the global protocol.

The analysis windows for on-treatment study assessments, including HBV DNA, HBV pgRNA, HBsAg, HBeAg, HBcrAg, adverse events, and clinical laboratories (chemistry, hematology, coagulation, urinalysis) are provided in [Table 3-1](#).

Table 3-1. On-Treatment Analysis Visit Windows for Study Assessments

Nominal Visit	On-Treatment Nominal Study Day	Visit Window Study Day	
		Lower Limit	Upper Limit
Day 1	1	(none)	1
Week 2	14	2	21
Week 4	28	22	42
Week 8	56	43	70
Week 12	84	71	98
Week 16	112	99	126
Week 20	140	127	154
Week 24	168	155	182
Week 28	196	183	210
Week 32	224	211	238
Week 36	252	239	266
Week 40	280	267	294
Week 44	308	295	322
Week 48	336	323	350
Week 52	364	351	378
Week 56	392	379	406
Week 60	420	407	434
Week 64	448	435	462
Week 68	476	463	490

Nominal Visit	On-Treatment Nominal Study Day	Visit Window Study Day	
		Lower Limit	Upper Limit
Week 72	504	491	≥504

The analysis windows for electrocardiograms (ECG) measurements are provided in [Table 3-2](#).

Table 3-2. On-Treatment Analysis Visit Windows for ECG

Nominal Visit	On-Treatment Nominal Study Day	Visit Window Study Day	
		Lower Limit	Upper Limit
Day 1	1	(none)	1
Week 12	84	2	126
Week 24	168	127	210
Week 36	252	211	294
Week 48	336	295	378
Week 60	420	379	462
Week 72	504	463	≥504

The analysis windows for off-treatment study assessments, including HBV DNA, HBV pgRNA, HBsAg, HBeAg, HBcrAg, vital signs, concomitant medications and adverse events, chemistry, hematology, coagulation and urinalysis are provided in [Table 3-3](#).

Table 3-3. Off-Treatment Analysis Visit Windows for Study Assessments

Nominal Visit	Off-Treatment Nominal Study Day	Visit Window Study Day	
		Lower Limit	Upper Limit
FU-Week 4	28	1	42
FU-Week 8	56	43	70
FU-Week 12	84	71	≥84

The analysis windows for ECG is provided in [Table 3-4](#).

Table 3-4. Off-Treatment Analysis Visit Windows for ECG

Nominal Visit	Off-Treatment Nominal Study Day	Visit Window Study Day	
		Lower Limit	Upper Limit
FU-Week 12	84	1	≥84

3.6.3. Selection of Data in the Event of Multiple Records in an Analysis Visit Window

Depending on the statistical analysis method, single values may be required for each analysis window. If a single value is needed, but multiple valid, nonmissing measurements exist in an analysis window, records will be chosen based on the following rules:

- For Baseline, the last nonmissing value on or prior to the first dose date of study drug will be selected, unless specified differently. If there are multiple records with the same time or no time recorded on the same day, the baseline value will be the average of the measurements for continuous data, or the measurement with the lowest severity for categorical data (eg, normal will be selected over abnormal for safety ECG findings).
- For postbaseline values:
 - The record closest to the nominal day for that visit will be selected with the exception of virology parameters in which the latest record will be selected. For the virology parameters, the later record will be selected.
 - If there are 2 records that are equidistant from the nominal day, the later record will be selected.
 - If there is more than 1 record on the selected day with the same time, the retest record will be selected.

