7.8.4 Electrocardiograms

A standard 12-lead ECG will be obtained as specified in the Schedule of Assessments ([Appendix 1](#)). Prior to the conduct of the 12-lead ECG, subjects should rest in a supine position for 10 mins. ECGs should be conducted in accordance with local practice and equipment. The ECG assessment will include interpretation of the tracings (eg, rhythm, presence of arrhythmia or conduction defects, morphology, any evidence of myocardial infarction, or ST segment, T-wave, and Uwave abnormalities). The Investigator or a physician Sub-Investigator is responsible for reviewing and overreading the ECG interpretation, for assessing whether the ECG machine interpretation findings are accurate, appropriate,

normal or abnormal, and for providing corrected interpretations as appropriate. In addition, any abnormal ECGs will be assessed for clinical significance.

Additional ECGs may be obtained if clinically indicated and will be obtained if abnormal and clinically significant or thought to be an error (eg, lead placement error, movement artifact, etc.). Any additional relevant data obtained by the Investigator during the course of this study will be recorded in the subject's source documentation. The Investigator or a physician Sub-Investigator will review all ECGs, evaluate the results, and sign/date the tracing or report. For any ECG abnormality that the Investigator considers clinically significant, the Investigator will:

- Repeat the ECG;
- Obtain follow-up ECG(s) if any significant abnormalities are detected after study drug administration to document resolution and as clinically indicated;
- Record as an AE any ECG abnormality that: (1) is confirmed and the Investigator considers clinically significant; (2) requires a subject to be discontinued from the study; or (3) the abnormality requires a subject to receive treatment. ([Section 8](#)).

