7.2.1.2. Summaries of Laboratory Abnormalities

A summary (number and percentage of subjects) for treatment-emergent graded laboratory abnormalities will be provided by lab test and treatment group; subjects will be categorized according to the most severe postbaseline abnormality grade for a given laboratory test:

For all summaries of laboratory abnormalities, the denominator is the number of subjects with nonmissing postbaseline values up to 28 days after last dose date of ABI-H2158/PBO.

The maximum postbaseline grade observed up to 28 days after last dose date will be tabulated for each laboratory test, and percentages will be based on the number of subjects with a postbaseline evaluation of the specific laboratory test.

Graded lab abnormalities will be also be summarized for the off-treatment period. Lab abnormalities are included starting from 29 days after the last dose of ABI-H2158/PBO.

A by-subject listing of graded laboratory abnormalities will be provided by subject ID number and visit in chronological order. This listing will include all test results that were collected throughout the study for the lab test of interest, with all applicable severity grades displayed.

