7.5. Electrocardiogram Results

A shift table of the Investigators' assessment of ECG results at each visit compared with baseline values will be presented by treatment group using the following categories:

- normal

- abnormal (not clinically significant)
- abnormal (clinically significant)
- missing/not done

The number and percentage of subjects in each cross-classification group of the shift table will be presented. Subjects with a missing value at Baseline or postbaseline will not be included in the denominator for percentage calculation.

A by-subject listing for ECG assessment results will be provided by subject ID number and visit in chronological order.

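### An abnormal for-cause ECG can drop out of the only by-arm ECG table, because SAP 3.6.3 keeps one tracing per 84- to 125-day (or open-ended) window

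*Combined protocol and SAP*

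**What the plan says.** SAP 7.5 plans one ECG table, a shift table in which the Investigators' "assessment of ECG results at each visit compared with baseline values will be presented by treatment group". The categories are normal, abnormal not clinically significant, abnormal clinically significant, and missing. A by-subject listing accompanies it.

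SAP 3.6.3 governs the case where "If a single value is needed, but multiple valid, nonmissing measurements exist in an analysis window". Its postbaseline rule is "The record closest to the nominal day for that visit will be selected", with only virology parameters exempt, followed by "If there are 2 records that are equidistant from the nominal day, the later record will be selected". If two records share the selected day and time, the retest is used.

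SAP Table 3-2 sets the on-treatment ECG windows. The first row (visit, nominal day, lower limit, upper limit) reads "Week 12 84 2 126". Table 3-4 puts all off-treatment ECGs in one FU-Week 12 window that opens on follow-up Day 1 and has no upper limit.

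Protocol 7.4 schedules on-treatment ECGs at Weeks 12, 24, 36, 48, 60 and 72. Protocol 7.8.4 adds: "Additional ECGs may be obtained if clinically indicated and will be obtained if abnormal and clinically significant or thought to be an error". Protocol 7.7 includes an ECG at the Premature Termination visit.

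For laboratory tests, by contrast, SAP 7.2.1.2 says "subjects will be categorized according to the most severe postbaseline abnormality grade for a given laboratory test".

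**The concern.** A by-visit shift table needs one category per subject per visit, so the selection rule decides which tracing is counted. Unscheduled ECGs are mostly taken because something looked wrong, yet they compete with a routine tracing that sits by design close to the nominal day. A rule based on distance from that day will usually keep the routine tracing. The records displaced are likely to be richer in abnormal findings than those kept.

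The laboratory tables, the adverse event severity tables and the individual liver-test summaries each carry a most-severe value. The ECG table has no such entry. Safety is a primary objective, and the trial stopped on a safety finding, so a reader may well take the shift table as the account of ECG abnormality by arm. It would not answer how many subjects per arm ever had an abnormal postbaseline tracing.

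**Working it through.** **Does the rule cover ECGs?** SAP 7.5 does not cite 3.6.3. However, 3.6.3 exempts only virology, its Baseline rule uses safety ECG findings as the example, and Table 3-2 is specific to ECGs. SAP 3.6.2 assigns observations to windows without excluding unscheduled ones. The rule applies.

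**Window widths** (upper − lower + 1, Table 3-2):
- Week 12: 126 − 2 + 1 = 125 days
- Week 24: 210 − 127 + 1 = 84 days
- Weeks 36, 48 and 60 (Days 211–294, 295–378, 379–462): 84 days each
- Week 72: Day 463 onward; 504 − 463 + 1 = 42 days up to and including the nominal day, then no limit

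**Days on which a for-cause ECG is displaced.** Take one scheduled ECG k days from the nominal day and one extra ECG on any other day of the window (width − 1 possible days).
- Scheduled ECG on the nominal day: no extra ECG on another day can be closer, so all are displaced.
- Scheduled ECG k days early: the extra ECG survives on the 2k − 1 days strictly closer, plus the one tied later day, making 2k days.
- Scheduled ECG k days late: it survives on 2k − 1 days only, because the tied day is earlier.

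Protocol 7.4 allows ±3 days through Week 24 and ±5 days from Week 28.

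| Window | Possible days | Displaced, on nominal day | Displaced, earliest allowed | Displaced, latest allowed |
|---|---|---|---|---|
| Week 12 (k = 3) | 124 | 124 | 118 (95%) | 119 (96%) |
| Week 24 (k = 3) | 83 | 83 | 77 (93%) | 78 (94%) |
| Weeks 36, 48, 60 (k = 5), each | 83 | 83 | 73 (88%) | 74 (89%) |

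Over Days 2 to 462 the possible days are 124 + 4 × 83 = 456. With every scheduled ECG as early as allowed, 118 + 77 + 3 × 73 = 414 are displaced (414/456 = 91%). With every one as late as allowed, 119 + 78 + 3 × 74 = 419 (92%). With every one on the nominal day, 456 (100%).

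**Same-day repeats.** A repeat on the day of the scheduled ECG is equidistant from the nominal day, so the later record replaces the tracing that prompted it. If the recorded times are identical, the retest is taken.

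**Off-treatment.** A Premature Termination ECG taken after the last ABI-H2158/PBO dose falls in FU-Week 12 (nominal follow-up Day 84). It loses to any later ECG nearer that day and is kept if there is none.

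**What escapes the table but is still reported.** Protocol 7.8.4 makes an ECG abnormality an adverse event if it is confirmed and clinically significant, needs treatment, or requires discontinuation. If treatment-emergent, it appears by arm in the SAP 7.1.6 tables. All ECG results are listed by subject. That leaves abnormal tracings that were unconfirmed or judged not clinically significant, with no by-arm count.

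**The case against.** The strongest reply is that the plan delivers what was promised. Protocol 10.4.4 calls for ECG findings by visit and treatment, and no document promises a worst-case ECG summary. Vital signs are handled by visit in the same way. The SAP is deliberately cut to key endpoints for a synoptic report, and the important findings reach the adverse event tables. Replacing a tracing is also right when it was a technical error, and a repeat that confirms an abnormality is itself abnormal, so the category survives. All of this stands, and it makes the point a modest one.

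Three stronger readings are tempting, and the documents do not support them:
- **That for-cause ECGs always drop out.** Loss requires another ECG in the window that is closer, or tied and later. If the scheduled ECG was missed, or the subject stopped before it, the for-cause ECG is kept. Early termination makes truncated last windows likely.
- **That the displacement floor is 93%.** Applying ±3 days at every visit gives 118 + 4 × 77 = 426 of 456. The protocol allows ±5 days from Week 28, which lowers it to 91%.
- **That the treatment comparison is shown to be biased.** The rule is the same in both arms and sites are blinded. It can hide abnormal tracings; a difference between arms in how many are hidden cannot be derived from the documents.

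**Conclusion.** The point holds in conditional form. As written, the plan can leave an abnormal for-cause or unconfirmed tracing out of its only by-arm ECG table, and usually will when the scheduled ECG in that window was done on time: 91% to 100% of possible days overall, 88% at the lowest in a single window.

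These are calendar days, not ECGs. They assume that every scheduled ECG through Week 60 took place and that the visit tolerance is centred on the SAP nominal day. For-cause ECGs need not be spread evenly over days, and their frequency is not given, so no number of lost tracings or affected subjects follows. The loss is from the table, not from the listing or from adverse event reporting. It is confined to abnormal tracings that were unconfirmed or judged not clinically significant. This is worth correcting because the remedy is cheap; it does not undermine the safety analysis as a whole.

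**What to change.** Keep the by-visit shift table in SAP 7.5 and add a worst-postbaseline-assessment row, cross-tabulated against Baseline by treatment group. For each subject take the most severe Investigator category (normal, abnormal not clinically significant, abnormal clinically significant) over all scheduled, unscheduled, repeat and Premature Termination ECGs. Show it separately for the on-treatment and off-treatment periods as SAP 3.6.2 defines them, so that Premature Termination ECGs after the last dose are covered. State in SAP 3.6.3 that closest-record selection does not apply to this row, and exclude tracings documented as technical errors.

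The cost is a sentence or two in the SAP and one added row per period, from data already collected. There is a small downside: some unconfirmed tracings will be counted, and a worst-of-all row depends on how many ECGs each subject had. A footnote giving the number of ECGs per subject by arm, with the by-visit table alongside, would let the reader judge that.

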7.5 Follow-up Assessments

All subjects who complete treatment per protocol or prematurely discontinue treatment will enter a 24-week follow-up period during which they will have the following assessments performed at 4, 8, 12, and 24 weeks (± 5 days) after the last dose of ABI-H2158 or PBO unless otherwise stated:

- Measure body weight (24 Weeks post only)
- Vital signs (temperature, heart rate, respiration rate and blood pressure)
- Complete physical examination (24 Weeks post only)
- Symptom-directed physical examination (not at 24 Weeks post)
- 12-lead ECG (24 Weeks post only)
- Review concomitant medications
- Review AEs
- Assess drug accountability (for ETV)
- Study drug dispensation (for ETV, 4 Weeks post and 12 Weeks post only)
- Laboratory analyses (additional details are provided in the Laboratory Manual):
 - Safety Labs: Chemistry, hematology, coagulation, urinalysis (4 Weeks post, 12 Weeks post, and 24 Weeks post only), and urine pregnancy test (if positive on dipstick, serum pregnancy test should be performed [4 Weeks post only]).
 - Virology/Immunology: HBV DNA, HBV pgRNA, HBsAg, HBeAg, HBcrAg, HBsAb and HBeAb (24 Weeks post only) sample for HBV sequencing and HBV nucleic acids
 - PK Sample: Sample for ETV can be collected at the same time with other labs (4 Weeks post only)

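### FU-Week 12 has no upper limit and virology takes the latest record, so any HBV DNA value after the 12-week follow-up visit replaces the true 12-week value

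*Combined protocol and SAP*

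**What the plan says.** **Day count and period.** SAP 3.6.1 defines the follow-up study day as "derived as Assessment Date – Last Dose Date of ABI-H2158/PBO". SAP 3.6.2 says the off-treatment "period is defined after the last dose of ABI-H2158/PBO through the follow up period". It sets no cut-off at 12 weeks.

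**Windows.** The last row of Table 3-3, which covers HBV DNA and the other virology markers, reads "FU-Week 12 84 71 ≥84" (nominal day, lower limit, upper limit). No row follows it. Table 3-4, for ECG, has a single row: "FU-Week 12 84 1 ≥84".

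**Selection.** When a window holds several post-baseline records, SAP 3.6.3 uses the one nearest the nominal day, "with the exception of virology parameters in which the latest record will be selected".

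**Visits.** Protocol 7.5 applies to completers and early stoppers alike, and has "the following assessments performed at 4, 8, 12, and 24 weeks". HBV DNA is taken at each of these visits. The only ECG scheduled in follow-up is at 24 weeks.

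**After termination.** SAP 1.2 reports that a clarification letter of 07 September 2021 shortened follow-up to 12 weeks. SAP 2.2 places the final analysis after the 12-week visits.

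**Output.** SAP 6.1.2 calls for descriptive statistics on HBV DNA, both observed values and change from baseline, for each arm and visit. SAP 6.2 drops the secondary efficacy analyses.

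**The concern.** Table 3-3 suits a study whose last follow-up visit is at week 12. The protocol, until September 2021, had a further visit at week 24, and it also allows unscheduled sampling in follow-up. The SAP gives such later records no window of their own, so they fall into FU-Week 12, where the latest-record rule prefers them to the sample taken on time.

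The result is a mislabelled value, not just an unspecified detail. A reader of the FU-Week 12 row would take it as HBV DNA about 84 days after stopping ABI-H2158/PBO, while some entries could be from day 168 or another late day. In a planned placebo arm of 10, one such record carries 1/10 = 10% of the arm mean; in a planned active arm of 30, 1/30 = 3.3%.

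**Working it through.** The plan states no figure to reproduce here. The check applies its rules to the protocol's visit days and then asks who could have late records.

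1. **Scheduled visits.** Weeks 4, 8, 12 and 24 after the last dose fall on follow-up days 28, 56, 84 and 168 (24 × 7 = 168). The ±5-day visit window puts the last between 163 and 173.

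2. **Assignment by Table 3-3.**

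| Window | Days | Records in it | Virology rule (latest) | Rule for other data (nearest) |
|---|---|---|---|---|
| FU-Week 4 | 1–42 | 28 | 28 | 28 |
| FU-Week 8 | 43–70 | 56 | 56 | 56 |
| FU-Week 12 | 71 onward | 84, 168 | **168** | 84 |

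The selected HBV DNA value is 168 − 84 = 84 days past nominal. With the last visit on day 163 or 173, that record is again the one selected. If the 12-week visit was missed, day 168 becomes FU-Week 12 for every parameter in Table 3-3, whichever selection rule applies.

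3. **Who could have had a 24-week visit before follow-up was shortened.** The decision to stop was on 01 September 2021 and the letter is dated 07 September 2021.
 - 01 September 2021 − 168 days = 17 March 2021
 - 07 September 2021 − 168 days = 23 March 2021
 - With the visit window: 01 September − 173 days = 12 March; 07 September − 163 days = 28 March

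Only subjects whose last ABI-H2158/PBO dose was by about mid to late March 2021 qualify. Protocol 7.1.1 refers to subjects screened under Amendment 1, and SAP 1 dates Amendment 2 to 14 December 2020. Such early stoppers are therefore possible, but nothing shows that any exist.

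4. **Unscheduled samples.** Protocol 9.4 extends ALT follow-up into the post-treatment period and beyond the last follow-up visit when an elevation has not resolved. Protocol 7.6 includes HBV DNA among the minimum assessments at an unscheduled visit. Any such sample after the 12-week visit also displaces it: a record on day 100, for example, would replace the one on day 84.

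5. **Primary analysis.** The Week 24 ANCOVA uses on-treatment days 155–182, and the on-treatment period ends at the last ABI-H2158/PBO dose. No follow-up record can enter it.

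6. **With bounded windows.** The existing limits are midpoints: (28 + 56)/2 = 42 and (56 + 84)/2 = 70. The next is (84 + 168)/2 = 126. With FU-Week 12 at 71–126 and FU-Week 24 from 127, day 84 goes to FU-Week 12 and day 168 to FU-Week 24.

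7. **ECG.** The latest-record rule does not apply, so the nearest record is used. A lone 24-week ECG on day 168 is labelled FU-Week 12. If there is also a termination-visit ECG on, say, day 3, the distances are |3 − 84| = 81 and |168 − 84| = 84, so the day-3 tracing is the one reported as FU-Week 12.

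**The case against.** The best defence is that FU-Week 12 is the last planned visit of the shortened study, and that leaving the final window open is this SAP's convention: on-treatment Week 72 also ends at ≥504. For a subject followed only to week 12, with no later samples, the rule does no harm. This stands, and it limits the point to subjects with later records. It does not remove the point, because the on-treatment period is closed by the last dose, whereas nothing closes the off-treatment window at 12 weeks.

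The consequence is also modest. The output is descriptive, the secondary virology analyses are dropped, and by-subject listings sorted by date would show the true timing. That stands too.

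A reader might go further and infer that the mislabelling biases the comparison between arms, because early stopping and extra ALT visits would be commoner on ABI-H2158. The documents do not support this. Protocol 7.9.1 gives several other reasons for stopping, including the subject's wish, resistance and pregnancy. SAP 1 reports the liver signal only in connection with the September 2021 decision. Nothing describes those who stopped by March 2021. A shift in log10 HBV DNA cannot be computed either: it needs the share of late records and the change between weeks 12 and 24, and the documents give neither. Subjects also stay on ETV during follow-up.

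It is equally tempting to say that Table 3-4 has the same fault. It does not: the latest-record rule does not apply to ECG, and the protocol schedules no 12-week ECG that could be displaced. The ECG issue is one of labelling.

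**Conclusion.** The rule, as written, reports any HBV DNA value taken after the 12-week follow-up visit as FU-Week 12 and discards the 12-week value. For a scheduled 24-week visit the error in timing is 84 days (79 to 89 if that visit falls at an edge of its window and the 12-week visit is on day 84). The mechanism is certain from the text; its reach is not. The number of affected subjects is not stated and may be zero, so it should not be said that 24-week values were in fact reported this way. The Week 24 ANCOVA is not affected.

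Two assumptions are made. First, the by-visit summary in SAP 6.1.2 is taken to include the off-treatment visits, since Table 3-3 defines windows for HBV DNA there. Second, the clarification letter, which is not among the documents, is taken not to exclude records after week 12 from analysis.

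For ECG, the label FU-Week 12 covers any off-treatment tracing from day 1. This is a minor presentational fault in the shift table of SAP 7.5.

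**What to change.** For off-treatment data only:

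- In Table 3-3, set FU-Week 12 to days 71–126 and add FU-Week 24 from day 127 for subjects with later records.
- In SAP 3.6.3, take the off-treatment virology record nearest the nominal day. The cap alone would still let an unscheduled sample between the 12-week visit and day 126 replace the 12-week value.
- Leave the on-treatment virology rule unchanged. Altering it could change the value used for the Week 24 primary analysis, and this point gives no reason to do so.
- In Table 3-4 and the ECG shift table, label premature-termination and 24-week ECGs as such.

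A cap at day 98, matching on-treatment Week 12, would also recover the day-84 value. Without a later row, however, it would leave records from day 99 onward with no window, which sits badly with the statement in SAP 3.5.2 that all data are included.

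The cost is one or two extra table rows with few subjects, a sentence in the SAP and minor programming. No new data are needed.
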